**Department of Psychology**

**Faculty of Social Sciences**

**International Islamic University Islamabad**

**July 10, 2024**

## **Background of the study**

The aim of the present study was to adapt the CRA Islamically because it is very important to add the cultural and religious aspects which are fundamentally important for the treatment of SUD. In CRA, face to face interaction is required for intervention including eight sessions for focuses on the reality of client's social environment so that for learning real life opportunities could be focused as per client needs to enhance engagement and learning (Godley, 2001).

For internal motivation and involvement in CRA, adaptations were added to enhance CRA's effectiveness. There were two major adaptations in CRA to make it accord with the cultural relevant with the targeted population. First adaptation is based on religion Islam. It includes several sections, and these sections are adapted in CRA's counseling goals. In first section morality was adapted with CRA, morality is about the Islamically integrated ways about hygiene, sleep, eating, clothes, meeting others, physical health, happiness and sadness related (Abbass, 2017). Second section was related to internal framework of human psyche, which comprises of Cognition (Aql), Behavioral inclinations (Nafs), Spirit (Ruh), Emotions (Ihsaas) and Heart (Qalb) (Keshavarzi & Khan, 2018). In third section principle of change, behavioral modification and tazkia-e-nafs were added along with three stages in principle of change: Inkishaf, itidal and Itehad (Keshavarzi & Khan, 2018).

## **Objectives:**

- To investigate whether IICRA has the better efficacy in treating substance dependence along with comorbidities than the indoor conventional treatment for substance dependence.
- To adapt the IICRA treatment strategy grounded in Pakistani culture and religious values for the treatment of drug addicts in Pakistan.

- To determine whether IICRA treatment is more effective in treating poly drug addicts and drug addicts with or without comorbidities.
- To determine whether IICRA treatment is more effective for those addicts who were treated for one or more treatment previously as compare to those having first treatment.

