The treatment group received interventions based on Islamically Integrated CRA (IICRA). These sessions were divided into daily goals including counseling related to hygiene, physical activities, psychotherapy of mental disorders and drug addiction related management. After discharge from residential treatment, they were followed up for six months to check the effectiveness of IICRA in the context of relapse and recovery from SUD as well as from comorbidities. These six months follow up was consist of further three follow up sessions; first session was conducted on the discharge date from the facility, second was on fifth month and third was on sixth month following discharge.

Sample in the present study for clinical trial was based on those diagnosed individuals who were hospitalized in rehab for the treatment of SUD. Age of the sample was varying from 16 years to 60 years, where 24% individuals were from late adolescence, 39% from early adulthood and finally 37% were from middle adulthood. The chronicity of disease in the sample varies 78% of them were abusing substance between from one year to 10 years and 22% were abusing more than 10 years. Similarly, the rate of relapse or number of treatments within sample was computed as 54% individuals were hospitalized first time and 46% were hospitalized two and more than two times. Additionally, the type of substance abuse was also varying cross the

sample which included cannabis, alcohol, pills, heroin, Ice and multiple substance abuse (Alcohol, cannabis and prescribed substances) as well. The gender was mainly male in sample which was 98% and only one participant was female in the sample. Moreover, 75% individuals of the sample were diagnosed with SUDs and 25% were also having comorbid mental illness. Hence, the representativeness of the sample was limited to clinical population diagnosed with SUDs as well as comorbidities with SUDs.

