**ADAPTATION OF COMMUNITY REINFORCEMENT APPROACH FOR
THE TREATMENT OF DRUG ADDICTION**

[name]

74-FSS/PHDPSY/F-18

[name]

Associate Professor (supervisor)

Department of Psychology

Faculty of Social Sciences

International Islamic University Islamabad

July 10, 2024

Statistical Analysis Plan

The collected data for this clinical trial was analyzed using SPSS 25 version. Important statistical analysis includes independent sample t-test, paired sample t-tests and one way ANOVA was used. Following are the defining parameters.

Independent sample t-test

Independent sample t-test was used to understand the efficacy of the treatment program between control and experimental groups.

Paired sample t-test

Paired sample t-test was used to elaborate the differences between the level of assessment. In order to assess the differences on pre and post assessment of interventions based on SCL-90 (scale of comorbidity).

One way ANOVA

One way ANOVA was used to understand the differences between pre assessment, post assessment and follow up to draw conclusion about the recovery of the participants which is measured by ARQ (Addiction recovery questionnaire).

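### The third objective asks about IICRA in poly-drug patients, but no analysis listed in the SAP uses substance type, so that part of the objective is untested

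*Protocol*

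**What the plan says.** The third item under Objectives in the Protocol reads "To determine whether IICRA treatment is more effective in treating poly drug addicts and drug addicts with or without comorbidities". This point concerns the poly-drug part only, that is, whether "IICRA treatment is more effective in treating poly drug addicts". No comparator is given for it, whereas the fourth objective does name one (patients in their first treatment).

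The sample description under Research Method and Design shows that substance type was noted. It refers to a "sample which included cannabis, alcohol, pills, heroin, Ice and multiple substance abuse (Alcohol, cannabis and prescribed substances) as well". It gives percentages for age group, duration of use, number of treatments and comorbidity, but none for the multiple-substance category.

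The SAP opens its list with "Important statistical analysis includes independent sample t-test, paired sample t-tests and one way ANOVA was used" and then gives each test a purpose:

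- Independent t-test: "Independent sample t-test was used to understand the efficacy of the treatment program between control and experimental groups".
- Paired t-test: pre versus post assessment, on the SCL-90.
- One-way ANOVA: "One way ANOVA was used to understand the differences between pre assessment, post assessment and follow up", on the ARQ.

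Neither document describes any other analysis.

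**The concern.** An objective about a particular kind of patient needs an analysis in which that characteristic appears as a subgroup, a stratum or an interaction term. Here it appears in none. The only between-arm test pools all patients. Poly-drug patients contribute to that pooled mean, but their response cannot be told apart from everyone else's.

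Two gaps make this harder to repair informally. First, without a comparator the target contrast is open, and the two natural readings call for different estimates. Second, the multiple-substance category is described as alcohol, cannabis and prescribed substances, with heroin and Ice listed separately. A patient using heroin together with cannabis could be classified either way.

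What is at stake is a stated objective, not the main comparison. With no contrast or grouping fixed in the plan, any conclusion about poly-drug patients would rest on choices that the plan does not constrain.

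**Working it through.** **Step 1: match the objective to the listed tests.**

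| SAP test | Factor | Outcome named | Uses substance type? |
|---|---|---|---|
| Independent t-test | Arm | None named | No |
| Paired t-test | Time (pre, post) | SCL-90 | No |
| One-way ANOVA | Time (pre, post, follow-up) | ARQ | No |

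The one-way ANOVA is the test that could have compared substance groups, but the SAP assigns it to assessment time.

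**Step 2: does the gap depend on how the objective is read?**

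- Reading A: IICRA versus usual treatment among poly-drug patients. This needs the arm difference within that stratum.
- Reading B: a larger IICRA effect in poly-drug than in single-substance patients. This needs the arm-by-poly-drug interaction.

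Both need substance type in the analysis, so the gap exists under either.

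**Step 3: what precision would an added analysis have?** The plan states no figure for this question, so there is nothing to reproduce first.

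Inputs from the Protocol (Research Method and Design): 28 of 34 control and 31 of 34 IICRA patients retained; 28 + 31 = 59, which agrees with the stated total at last follow-up.

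Assumptions, not in the documents: a poly-drug share p equal in both arms, taken from 20% to 50%; common SD of 1; two-sided 5%; no adjustment for baseline; 59 − 4 = 55 degrees of freedom, so t = 2.004.

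Formulas, in SD units:

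- Interaction SE = √[1/(28p) + 1/(28(1−p)) + 1/(31p) + 1/(31(1−p))]
- Stratum SE = √[1/(28p) + 1/(31p)]
- 95% half-width = 2.004 × SE

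Interaction at p = 20%: the cells are 5.6, 22.4, 6.2 and 24.8. SE = √(0.1786 + 0.0446 + 0.1613 + 0.0403) = √0.4248 = 0.652. Half-width = 2.004 × 0.652 = 1.31.

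Interaction at p = 50%: the cells are 14, 14, 15.5 and 15.5. SE = √(2/14 + 2/15.5) = √0.2719 = 0.521. Half-width = 2.004 × 0.5214 = 1.04.

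| Assumed share | Interaction half-width | Interaction detectable at 80% power | Stratum half-width |
|---|---|---|---|
| 20% | 1.31 SD | 1.86 SD | 2.004 × √(1/5.6 + 1/6.2) = 1.17 SD |
| 30% | 1.14 SD | 1.62 SD | 2.004 × √(1/8.4 + 1/9.3) = 0.95 SD |
| 50% | 1.04 SD | 1.49 SD | 2.004 × √(1/14 + 1/15.5) = 0.74 SD |

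The detectable differences use the noncentral t distribution. For comparison, the whole-sample contrast of 28 with 31 detects about (1.960 + 0.842) × √(1/28 + 1/31) = 2.802 × 0.261 = 0.73 SD at 80% power (normal approximation).

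**The case against.** **The SAP list may not be complete.** It is introduced as including the important analyses, so others could exist. That is fair as to wording, but no further analysis is described in either document, so none is pre-specified for this question.

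**The objective need not be an interaction question.** A reader might infer that only a test of effect modification could answer it. The documents do not support that: with no comparator named, a within-stratum arm difference is an equally natural target. This objection stands and shapes the fix.

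**Stronger readings go too far.** A reader might infer that the SAP's results would be identical whatever happened to poly-drug patients. They would not be, since those patients shift the pooled mean. A reader might also infer that the investigators will read the answer off the whole-sample result. That is a plausible risk, because it is the only between-arm test, but neither document says so.

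**The data may not allow a clean coding.** The Protocol shows a list of categories, not every substance used by each patient. The bracketed description may simply record what was seen in this sample. Both points stand, so one cannot assume that all combinations were recorded.

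**Arm and site coincide.** All IICRA patients come from one clinic and all controls from the other (Research Method and Design). An arm-by-poly-drug term is equally a site-by-poly-drug term. This stands and must be stated with any result.

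**Little would be learned.** The intervals are wide, and the Protocol already reports final retention, so the analysis may be post hoc. That supports an exploratory label. It does not justify leaving an objective with neither an analysis nor a statement that it was untested.

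**Conclusion.** The concern holds in this form: no listed analysis uses substance type, so the poly-drug part of the third objective is untested under either reading of it. This rests on the text alone and needs no assumption.

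The size of the precision problem does rest on assumptions. For an assumed equal share of 20% to 50%, the interaction would be estimated to within about ±1.31 to ±1.04 SD, and the within-stratum arm difference to within about ±1.17 to ±0.74 SD. These figures are for an unadjusted four-cell contrast. Adjusting for pre-assessment ARQ would cost one degree of freedom and could narrow the intervals, by an amount that depends on a correlation the documents do not give. Unequal shares between arms would also change them.

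The gap should be corrected, but it does not affect the main comparison. It does not follow that the question is unanswerable in principle: an exploratory estimate is possible if the records identify poly-drug patients.

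**What to change.** In the SAP:

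1. State which contrast the objective means: IICRA versus usual treatment within poly-drug patients, a larger effect in them than in single-substance patients, or both.
2. Code poly-drug as two or more recorded substances where the records allow; otherwise use the recorded multiple-substance category and say so. Give poly-drug counts by arm.
3. Add one model, labelled exploratory: follow-up ARQ on arm, pre-assessment ARQ, poly-drug (yes/no) and arm × poly-drug. Name the follow-up assessment used.
4. Report the arm difference within poly-drug patients and the interaction, each with a 95% confidence interval.
5. Base any statement about benefit within poly-drug patients on the stratum estimate, and any statement about greater benefit than in other patients on the interaction. If the relevant interval includes zero, report that question as not determined.
6. State that arm coincides with site, so both estimates also carry site differences.

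The cost is SAP wording, one extra model and a check of what was recorded for each patient; that check may take more work if combinations were not captured. The downside is a wide interval and a less favourable statement on the third objective. If the coding cannot be done, report this part of the objective as untested.

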### **Research Method and Design:**

A randomized control trial was used as research method on indoor residential patients and guidelines of good clinical practices were followed (Guideline, 2001). The sample size for this clinical trial was 60 in total (30 for control group and 30 for treatment group) in order to maintain this number, the sample size was extended to 34 for each group in order to get adequate retention of the sample. The retention number of sample was 68 at the time of pre assessment and closed at 59 at the time of last follow up assessment. All participants who were admitted for treatment of SUD with or without comorbid mental disorders were recruited for research. Intervention was administered after the 21 days of detoxification. For recruitment and randomization, it was not applicable to control extraneous variables in a single facility so two sites were selected for this purpose. Selection of sites were based on minimizing extraneous variables by selecting identical residential treatment sites. One site such as Islamabad Rehab Clinic (IRC) was willing to give permission for implementation of IICRA based intervention. Hence, IRC was selected for recruiting treatment group.

Second site was considered for recruiting control group where they were giving traditional treatment in residential setting based on disease model. The site is named as Hayat Rehab Clinic (HRC). The permission for conducting research and recruiting participants were sought out from the authorities. Traditional treatment was termed as treatment as usual which includes detoxification of drugs and duration of detoxification from acute withdrawal consisted on 21 days,

During these early days focus was on adjustment to residential treatment along with hygiene and routine related compliance. Afterwards, the focus was on general counselling for drug addiction prevention, twelve steps program, habit formation based on seven habits for highly effective people and life skills training which is mainly delivered through group classes and lectures. Patients' individual sessions are also scheduled with psychologists once weekly, the focus of these individual sessions is to maximize the interaction with family through relationship building and relapse prevention skills. Duration of residential treatment is between 90-120 days.

The treatment group received interventions based on Islamically Integrated CRA (IICRA). These sessions were divided into daily goals including counseling related to hygiene, physical activities, psychotherapy of mental disorders and drug addiction related management. After discharge from residential treatment, they were followed up for six months to check the effectiveness of IICRA in the context of relapse and recovery from SUD as well as from comorbidities. These six months follow up was consist of further three follow up sessions; first session was conducted on the discharge date from the facility, second was on fifth month and third was on sixth month following discharge.

Sample in the present study for clinical trial was based on those diagnosed individuals who were hospitalized in rehab for the treatment of SUD. Age of the sample was varying from 16 years to 60 years, where 24% individuals were from late adolescence, 39% from early adulthood and finally 37% were from middle adulthood. The chronicity of disease in the sample varies 78% of them were abusing substance between from one year to 10 years and 22% were abusing more than 10 years. Similarly, the rate of relapse or number of treatments within sample was computed as 54% individuals were hospitalized first time and 46% were hospitalized two and more than two times. Additionally, the type of substance abuse was also varying cross the

sample which included cannabis, alcohol, pills, heroin, Ice and multiple substance abuse (Alcohol, cannabis and prescribed substances) as well. The gender was mainly male in sample which was 98% and only one participant was female in the sample. Moreover, 75% individuals of the sample were diagnosed with SUDs and 25% were also having comorbid mental illness. Hence, the representativeness of the sample was limited to clinical population diagnosed with SUDs as well as comorbidities with SUDs.

Secondly, the professionals who were providing treatment were not aware of the allocation of the individual in control and treatment group as well as the recruited individuals for the clinical trial. They were responsible for conducting sessions and recording those sessions through treatment forms as well as monitoring the goals whether desired goal is achieved or not. They were also given the treatment protocol schedule for effective treatment adherence. Additionally, panel assessments were planned at both sites for reviewing and addressing treatment related issues faced by professionals as well as the achievement of desired goals of the treatment. These panel assessments were carried out by weekly to ensure the engagement of the patients, adherence and fidelity to the treatment protocols. This committee was comprised of four professionals having experience in the treatment planning and execution with the minimum educational level of MS in Clinical Psychology.

Moreover, for the purpose of comparability of results and to control the extraneous variables, two treatment sites were selected for clinical trial. Both sites were equal in terms of organizational structure which includes residential treatment facility for mental health, same geographical region with outdoor areas, hierarchy of professionals, daily routine of the patients, psychiatrist consultation, outdoor and indoor activities of the patients and length of residential

treatment. The professionals engaged in the clinical trial has similar qualification and experience at both facilities.

During this clinical trial, 28 out of 34 participants were retained in control group and successfully completed the duration of clinical trial. Three participants had withdrawn the treatment after 40 days of hospitalization and one individual passed away after discharge from rehab. Remaining two participants did not continue the follow up sessions.

Similarly, in experimental group 31 participants out of 34 had successfully completed the Treatment duration for clinical trial. Two participants had withdrawn the treatment after a month of admission and one participant did not continue after the discharge from the facility.

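### The SAP names no analysis set and no rule for missing scores, so any last-follow-up analysis run as written rests on at most 59 of 68 patients

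*Protocol*

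**What the plan says.** The protocol, under Research Method and Design, reports the overall flow: "The retention number of sample was 68 at the time of pre assessment and closed at 59 at the time of last follow up assessment". It accounts for every loss by arm. In the control group, "Three participants had withdrawn the treatment after 40 days of hospitalization and one individual passed away after discharge from rehab", and "Remaining two participants did not continue the follow up sessions". In the IICRA group, two patients withdrew during residential treatment and one was not followed beyond discharge. The only provision for loss in either document is over-recruitment from 30 per group: "the sample size was extended to 34 for each group in order to get adequate retention of the sample".

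The SAP names three tests:

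- Between groups: "Independent sample t-test was used to understand the efficacy of the treatment program between control and experimental groups". Neither the scale nor the time point is given.
- Within patients, a paired t-test: "In order to assess the differences on pre and post assessment of interventions based on SCL-90 (scale of comorbidity". No follow-up visit is mentioned for this scale, and the timing of the post assessment is not defined.
- Over time, for the ARQ: "One way ANOVA was used to understand the differences between pre assessment, post assessment and follow up".

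Neither document states who is analysed, what happens when a score is missing, how the death is treated, or any sensitivity analysis.

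**The concern.** Each named test needs an observed score, or a pair of them. With no other rule, a patient without the score drops out. A paired test loses anyone lacking either score. The ANOVA, run as complete-case repeated measures, keeps at most 59 patients; run as independent groups, it compares up to 68 entry scores with at most 59 at the last follow-up.

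The six-month follow-up was there to show relapse and recovery. Withdrawing from treatment, breaking off contact or dying is plausibly related to that outcome, so the patients who drop out may not resemble those who remain. Extra recruitment replaces the lost numbers but cannot restore the comparison between those who were lost and those who stayed. As things stand, a reader cannot tell which patients any reported result describes.

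**Working it through.** **1. Reproduce the plan's figure of 59** (inputs: Protocol, Research Method and Design).

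- Control: 34 − (3 + 1 + 2) = 28.
- IICRA: 34 − (2 + 1) = 31.
- Total: 28 + 31 = 59, and 68 − 59 = 9 lost. The flow agrees exactly.

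**2. Is loss unequal?** 6/34 = 17.6% against 3/34 = 8.8%. Fisher's exact test on 6/28 against 3/31 gives p = 0.476. With nine events this neither shows nor excludes informative loss.

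**3. Which analyses does 59 describe?** Only those at the last follow-up. If the post assessment took place at discharge, and the five patients who withdrew were not assessed then (both assumptions), at most 68 − 5 = 63 would have a post score (31 control, 32 IICRA). The documents do not give the actual number.

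**4. How far could the arm difference move?** Set the death aside, leaving 33 control and 34 IICRA survivors, of whom 5 and 3 were lost. Let lost survivors differ from completers by an assumed *d* SD. Each arm mean then moves by *d* × (lost ÷ survivors), and the arm difference by

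- *d* × (5/33 − 3/34) = 0.063*d* if the gap has the same direction in both arms;
- *d* × (5/33 + 3/34) = 0.240*d* if the directions are opposite.

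| Assumed *d* (SD) | Same direction (SD) | Opposite directions (SD) |
|---|---|---|
| 0.25 | 0.02 | 0.06 |
| 0.5 | 0.03 | 0.12 |
| 1.0 | 0.06 | 0.24 |

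For scale, the standard error of the completer contrast, with SD set to 1, is √(1/28 + 1/31) = 0.261.

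**5. What would modelling all 68 gain in precision?** Assume SD 1, the same correlation *r* between all visits, separate arm means at every visit, only an entry score for the five who withdrew, and entry plus discharge scores for the four later losses. The variance of an arm's month-6 mean is then

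(1 − B)/n₆ + (B − A)/n_d + A/34, with A = *r*² and B = 2*r*²/(1 + *r*),

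where n_d is 31 (control) or 32 (IICRA) and n₆ is 28 or 31. At *r* = 0.5, A = 0.25 and B = 0.333:

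- control: 0.6667/28 + 0.0833/31 + 0.25/34 = 0.03385;
- IICRA: 0.6667/31 + 0.0833/32 + 0.25/34 = 0.03146;
- standard error: √0.06531 = 0.2556, against 0.2607 for completers, a reduction of about 2%.

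The same formula gives 0.2587 at *r* = 0.3 and 0.2512 at *r* = 0.7.

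**6. Side query on the sample description.** Its percentages carry no denominator. Searching sizes from 40 to 100 with ordinary rounding, only 59 fits all of them: ages 14/23/22, chronicity 46/13, first or repeat admission 32/27, without or with comorbidity 44/15, men 58/59 = 98.3%. Sizes 63 and 67 miss by one point. Size 68 misses by two: 27/68 rounds to 40% rather than 39%, and 67/68 = 98.5% rounds to 99% rather than 98%.

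**The case against.** The strongest reply is that harm is assumed rather than demonstrated. The losses are fully disclosed by arm and type, the difference in loss is compatible with chance, and every shift in the table is an assumed gap multiplied by a small fraction. Nothing in the documents suggests that the gap would run in opposite directions, and with a common direction a 0.5 SD gap moves the contrast by 0.03 SD, far inside the standard error. All of this stands, and it limits how much weight the point can bear.

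It is also fair that the mixed model is not the only repair. It gains about 2% in precision at *r* = 0.5, and under the assumptions above five of the nine losses contribute an entry score only. It also rests on missing at random, which is in doubt precisely if loss follows relapse; the sensitivity analysis is what addresses that worry. The least the SAP should do is name the analysis set and report the numbers per test.

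Three stronger readings are tempting and not supported:

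- A reader might infer that a completers-only analysis was chosen. The SAP does not say so; it is what the named tests do by default.
- A reader might apply 59 of 68 to every test. The SAP ties follow-up only to the ARQ and leaves the independent t-test undated.
- A reader might take the percentages as proof that the sample description omits the nine losses. Size 68 can still be reached by trimming the age figures to total 100 and truncating 98.5%.

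**Conclusion.** The omission is real: no analysis set, no rule for missing scores and no handling of the death, in a trial that lost 9 of 68 patients. The figure of at most 59 holds for last-follow-up analyses only.

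The consequence is a possible bias that is not shown, has unknown direction and is probably modest: 0.02 to 0.06 SD for an assumed gap of 0.25 to 1.0 SD running the same way in both arms, and up to 0.24 SD in the extreme opposite-direction case. The documents do not support a claim that the losses favoured IICRA, or that they changed any conclusion.

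This is not a matter of power: the completer standard error of 0.261 is close to the √(2/30) = 0.258 of the planned 30 per group. The point is worth acting on because the repair uses existing data and tells the reader who was analysed. The denominator query adds nothing to its weight.

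**What to change.** 1. **Analysis set and model.** State that all 68 are analysed in their original group, and report the number contributing to each test, visit and arm. For the ARQ, replace the one-way ANOVA with a likelihood-based repeated-measures mixed model that takes the entry score as one of the outcomes and uses all available later scores. Let each arm have its own mean at entry, because the arms came from different sites ("Hence, IRC was selected for recruiting treatment group"). State the missing-at-random assumption. For the SCL-90, use the same approach only over the visits at which it was actually measured. Say which scale and time point the independent t-test refers to.
2. **Sensitivity analysis.** Vary the assumed scores of the eight surviving losses separately by arm, for example by 0.25 to 1.0 SD in either direction. Report the control death separately.
3. **One-line query.** Confirm the denominator of the percentages in the sample description.

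Label all of this as added after data collection.

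The cost is some SAP wording, one model per scale and one sensitivity table; no new data are needed. The downside is that the estimate may become less certain or move either way, that missing at random cannot be checked from the data, and that the gain in precision is small. None of it addresses the recruitment of each arm from its own site.

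### The study is labelled randomised, but arm equals clinic and no random assignment is described, so the t-test cannot separate IICRA from the clinic that delivered it

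*Protocol*

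**What the plan says.** Every Protocol statement below is under Research Method and Design unless noted.

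- **Label.** "A randomized control trial was used as research method on indoor residential patients".
- **Randomisation.** The word appears once more, as a reason for using two clinics: "For recruitment and randomization, it was not applicable to control extraneous variables in a single facility so two sites were selected for this purpose". No sequence, unit, method or concealment is given for patients or for clinics.
- **Arms.** IRC agreed to host the intervention. "Hence, IRC was selected for recruiting treatment group". For the comparator: "Second site was considered for recruiting control group where they were giving traditional treatment in residential setting based on disease model".
- **Recruitment and retention.** "All participants who were admitted for treatment of SUD with or without comorbid mental disorders were recruited for research". "The retention number of sample was 68 at the time of pre assessment and closed at 59 at the time of last follow up assessment". Completers were 28 of 34 controls and 31 of 34 IICRA patients.
- **Patient mix.** It is given for both arms together, without a denominator. For example, on age: "24% individuals were from late adolescence, 39% from early adulthood and finally 37% were from middle adulthood"; on earlier treatment: "54% individuals were hospitalized first time and 46% were hospitalized two and more than two times".
- **Clinic comparability.** The two clinics are said to match in organisation, region, daily routine, length of stay, psychiatric consultation and staff qualification. No patient characteristic is given by clinic.
- **Blinding.** Treating professionals are said not to have known the allocation or who was in the trial, although they ran the sessions and held the treatment schedule.
- **Analysis.** The SAP (Independent sample t-test) compares control and experimental groups for efficacy. It names no covariate, time point or analysis set.

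**The concern.** Randomisation is what allows a difference between arms to be credited to treatment. Here the stated reason for IRC's role is its consent, not chance, and each treatment was given at one clinic only. A gap between arms could come from IICRA, from the patients each clinic admits, or from anything else that differs between the clinics.

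The first objective is that IICRA has better efficacy than conventional inpatient treatment. As written, a prognostic difference between the clinics' patients would be reported as that efficacy and read as randomised evidence. The reader has no by-clinic data with which to check for one. If the pooled description covers completers only, it is not a description of who entered.

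**Working it through.** **1. Arm and clinic are the same variable.** Code arm = 1 for IICRA and clinic = 1 for IRC. The two columns are identical, so a model with intercept, arm and clinic has three columns but rank 2. The treatment effect and the clinic effect cannot both be estimated. The t-test estimates their sum.

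**2. Denominator of the patient mix.** Completers: 28 + 31 = 59, which matches the Protocol. The table shows which whole-number counts round to each reported percentage under ordinary rounding.

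| Reported % | Count of 59 | Count of 68 |
|---|---|---|
| Age 24 | 14 (23.7) | 16 (23.5) |
| Age 39 | 23 (39.0) | none: 26 gives 38.2, 27 gives 39.7 |
| Age 37 | 22 (37.3) | 25 (36.8) |
| Use up to 10 years 78 | 46 (78.0) | 53 (77.9) |
| Use over 10 years 22 | 13 (22.0) | 15 (22.1) |
| First admission 54 | 32 (54.2) | 37 (54.4) |
| Repeat admission 46 | 27 (45.8) | 31 (45.6) |
| Male 98, one female | 58 (98.3) | none: 67 gives 98.5, which rounds to 99 |
| SUD only 75 | 44 (74.6) | 51 (75.0) |
| Comorbid 25 | 15 (25.4) | 17 (25.0) |

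All ten fit 59, and each set of categories sums to 59 (14 + 23 + 22 for age). With 68, eight fit and two do not. Among all N from 20 to 300, only 59 fits every figure with exactly one female. Loss was also unequal: 6/34 = 17.6% of controls and 3/34 = 8.8% of IICRA patients.

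**3. What the pooled figures allow.** The 27 repeat admissions among 59 fit any split from 27/31 v 0/28 to 0/31 v 27/28 (IICRA v control). One possibility is 18/31 v 9/28, that is 58% v 32%. The pooled total therefore says nothing about balance.

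**4. How often a clinic difference alone gives significance.** The documents give no SD and no clinic difference, so the shift δ (in SD units) is an assumption. With no IICRA effect, the t statistic is noncentral t with df = n1 + n2 − 2 and noncentrality δ / √(1/n1 + 1/n2). The root is √(1/31 + 1/28) = 0.261 and √(1/34 + 1/34) = 0.243. Two-sided 5% rejection rates:

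| Assumed shift (SD) | 31 v 28 | 34 v 34 |
|---|---|---|
| 0.1 | 6.6% | 6.9% |
| 0.2 | 11.7% | 12.8% |
| 0.3 | 20.5% | 23.0% |
| 0.5 | 47.0% | 52.9% |

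Both sizes are shown because the SAP does not say whether 59 or 68 are analysed. The smallest observed gap that reaches p < 0.05 is t(0.975) × √(1/n1 + 1/n2): 0.522 SD for 31 v 28 and 0.484 SD for 34 v 34.

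**5. Blinding against design.** Each clinic gave one treatment, and its staff delivered that treatment from a schedule. They would have known which treatment their patients received. The other half of the claim, that they did not know who was enrolled, is hard to reconcile with the statement that all admitted patients were recruited.

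**The case against.** - **The clinics were chosen to be alike.** The Protocol aims for identical sites and lists many shared features. This is relevant, but it is asserted without data and concerns organisation and staff, not patients.
- **A procedure may exist that was not written down.** The paragraph on blinding opens as the second point of a list with no visible first point, and it refers to allocation. This stands as a possibility, so the relabelling should depend on whether random assignment can be documented. Randomising within or between these two clinics would still have to be squared with the stated reason for choosing IRC.
- **The denominator is inferred.** No denominator is stated, and eight of ten percentages also fit 68. Age counts of 16/27/25 would round to 24/40/37, which sums to 101, so someone might have trimmed 40 to 39; the 98% would then need truncation as well. That takes two separate departures from ordinary rounding, whereas 59 needs none. The right word is apparently.
- **Only prognostic differences matter, and change scores would cancel stable differences in level.** True, but the SAP does not say that change scores are used, and they would not cancel differences in the course of recovery.
- **The shifts are assumed.** They are, and at 0.1 SD the error rate barely rises. The argument does not depend on any one value.
- **Staff may have been unaware only of trial roles.** At HRC, staff giving usual treatment might not have known that their patients were controls. This is harder to accept at IRC, and the text does not make that distinction. The sentence on recruiting all admitted patients may also describe eligibility, which is why it needs reconciling.

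**Conclusion.** The concern holds and must be fixed. The randomised label is not supported by anything in the documents, arm and clinic coincide completely, and an unadjusted t-test cannot support a conclusion that IICRA itself is more effective. These points rest on the text alone.

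The size of any bias is unknown. The rejection rates illustrate it under assumed shifts in a standardised outcome with normal errors and equal variances. That the patient description covers completers only is a strong inference, not a stated fact. There is no evidence that the clinics' patients did differ; the point is that comparability at entry is not shown.

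**What to change.** 1. **Protocol, design label.** Unless a random assignment can be documented, describe the study as a non-randomised two-site controlled comparison with allocation by site. State the conclusion as IICRA at IRC versus usual treatment at HRC, and say that no analysis can remove the clinic effect.
2. **SAP, between-group analysis.** Replace the unadjusted t-test with a regression of the outcome on arm, adjusted for the pre-assessment score, first v repeat admission, comorbidity and years of use. Name the outcome, time point and analysis set. Label it post hoc, because follow-up is complete. The short covariate list suits a sample of this size; previous treatment and comorbidity are already named in the objectives.
3. **Protocol, sample description.** Add a table of the recorded characteristics by arm for all 68 enrolled, with the 59 completers alongside, and state each denominator.
4. **Protocol, blinding.** Withdraw the claim that treating professionals were unaware of treatment allocation. Keep the claim that they did not know who was enrolled only if it is reconciled with the recruitment of all admitted patients.

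The cost is wording, one regression and one table, assuming the characteristics were recorded at entry for all 68. The price is a weaker design label and a conclusion limited to two clinics. The adjusted estimate covers recorded characteristics only and still includes the clinic effect.
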